10.1 Best Corrected Visual Acuity

BCVA will be measured using ETRDRS method at each visit.

10.2 Corneal Epithelium Grading

Corneal epithelium grading, including the presence of SPK, will be recorded at each visit.

10.3 Intraocular Pressure

Intraocular pressure will be measured by tonometry at screening and at each visit.

10.4 Cataract Assessment

Cataract grading will be recorded at each visit.

10.5 Vital Signs

Vital signs will be recorded at each visit.

10.6 Adverse Events

10.6.1 Definition of Adverse Events

An adverse event is defined as any untoward medical occurrence in a patient or clinical investigation subject administered a pharmaceutical product and which does not necessarily have a causal relationship with this treatment.

10.6.2 Relationship to Study Drug

Relationship to study drug will be determined by the Investigator and so reported to the medical monitor.

10.6.3 Adverse Event Intensity Grading

The intensity of all AEs will be graded according to the following table:

Mild: AE requiring no special treatment and not requiring deviation from the usual activities
Moderate: AE that impairs usual activities but are ameliorated by simple therapeutic interventions
Severe: AE which impairs usual activities and requiring intervention

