2.3 SCH1

SCH1 is a novel combination anti-infective / steroid eye drop with *in vitro* efficacy against many bacteria, yeasts, fungi and human adenovirus. The product contains two FDA-approved active pharmaceutical ingredients (Pred Forte, or prednisolone acetate 1%, application #017011, approved May 30, 1973; chlorhexidine gluconate, approved December 28, 1995). The combination is formulated as a 0.2% chlorhexidine 1% prednisolone acetate ophthalmic suspension. In preclinical evaluation, it demonstrated antimicrobial efficacy on contact with ocular isolates of *S.aureus*, *P. aeruginosa*, *E. coli*, *C. albicans*, and *A. brasiliensis*. A review of preclinical studies is provided in the investigators brochure.

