6.4 Subject Rescue Criteria and Procedures

Subjects who experience onset of a corneal infiltrate, intraocular inflammation, or glaucoma are to receive rescue therapy. Dosing with SCH1/placebo is to be stopped at the time of administration of rescue therapy. All evaluations scheduled for visit 3/End of Treatment should be performed at this time.

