10.0 Assessment of Safety

The safety population is defined as all subjects who received one or more doses of SCH1. Standard summary and/or analysis techniques will be used for the evaluation of AEs, vital sign measurements, clinical laboratory results and physical examinations, and these are to be detailed within the body of the report. The safety data will be presented in individual listings and summary tables where appropriate.

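### The AE intensity table in section 10.6.3 leaves two kinds of event without a grade and does not clearly separate moderate from severe

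*Combined protocol and SAP*

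**What the plan says.** Section 10.6.3 applies to every event without exception: "The intensity of all AEs will be graded according to the following table". The table has three rows:

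- The lowest grade sets two conditions, both of which must hold: "Mild: AE requiring no special treatment and not requiring deviation from the usual activities".
- The middle grade joins impairment to the response to treatment: "Moderate: AE that impairs usual activities but are ameliorated by simple therapeutic interventions".
- The highest grade joins impairment to a need for treatment: "Severe: AE which impairs usual activities and requiring intervention".

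The section gives no tie-break, no worst-grade rule and no separate scale for examination findings. Section 10.6.4 counts events that the investigator observes as well as those the subject reports, so a finding without complaints is in scope.

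Three other places bear on the point. Section 2.3 describes the product: "The combination is formulated as a 0.2% chlorhexidine 1% prednisolone acetate ophthalmic suspension". Section 10.3 provides for pressure readings: "Intraocular pressure will be measured by tonometry at screening and at each visit". Section 6.4 names events that lead to treatment: "Subjects who experience onset of a corneal infiltrate, intraocular inflammation, or glaucoma are to receive rescue therapy". On analysis, section 10.0 says only: "Standard summary and/or analysis techniques will be used for the evaluation of AEs".

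**The concern.** An ordinal scale that must be applied to all events should give each event exactly one grade. This one uses impairment and treatment together, and the rows pair them in only some of the possible ways. Where no row fits, the grader must leave the grade blank or force one. Where two rows fit, the choice is the grader's.

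This is more than a drafting nicety here because the product contains a steroid and the trial looks for ocular findings by tonometry and slit lamp. Such findings can call for treatment before they affect what the subject can do, and that is one of the combinations without a grade. At stake is whether a table of AEs by intensity means the same thing from one event to the next.

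**Working it through.** The plan gives no figure on this point, so there is nothing to recompute. The check is to set the three definitions against the possible combinations of impairment and treatment.

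**Inputs, all from section 10.6.3**

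- Mild: no special treatment needed, and no departure from usual activities.
- Moderate: activities impaired, and the event is relieved by simple therapeutic measures.
- Severe: activities impaired, and intervention needed, of any kind.

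Impairment of activities and departure from them are taken to mean the same thing. Each combination is read twice. The literal reading takes each row on its own. The generous reading treats the rows as ordered steps and a simple measure as something less than special treatment.

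| Activities impaired | Treatment | Literal reading | Generous reading |
|---|---|---|---|
| No | None | Mild | Mild |
| No | Simple | Mild only if simple is not special | Mild |
| No | Special | No grade | No grade |
| Yes | None | No grade | No grade |
| Yes | Simple | Moderate and Severe | Moderate |
| Yes | Beyond simple | Severe | Severe |

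**What holds on both readings**

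1. *Special treatment, no impairment.* The treatment rules out Mild. The lack of impairment rules out Moderate and Severe. A pressure rise found by tonometry and treated, in a subject whose activities are not limited, is an example.
2. *Impairment, no treatment.* The impairment rules out Mild. With no measure giving relief, the event is not Moderate. With no intervention needed, it is not Severe. Blurring that stops reading for a while and clears by itself is an example.

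**What depends on the reading**

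3. *Impairment, relieved by a simple measure.* Moderate fits. If the measure was needed, Severe fits too, because that row sets no lower limit on the kind of intervention. The overlap goes if Severe is taken to mean more than a simple measure, but the text does not say that. An event that improves with a simple measure without strictly needing it could be Moderate only.
4. *No impairment, simple measure.* The Mild row excludes only special treatment, so this event can reasonably be graded Mild.

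The combinations classify definitions, not events. How many there are depends on how treatment is divided, so a count of defective ones would not measure the effect.

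**The case against.** The best defence is that the table is a familiar ordered scale and investigators will read it so. Moderate is marked off by relief from simple measures, so Severe naturally means something more. This weakens the overlap, and that part of the point should be put as unclear wording, not as contradiction. It does not fill the two gaps, which remain under the same generous reading.

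The second defence is that the important events are recorded elsewhere. This is largely right. The synopsis lists SPK, pressure and acuity loss as safety measures, and sections 10.1 to 10.3 provide for acuity, corneal grading and pressure at each visit. Section 6.4 brings forward the final evaluations at rescue, section 6.3 requires the reason for withdrawal in the CRF, and section 10.6.5 classifies seriousness separately. None of these supplies the missing intensity grade, but they mean that a treated pressure rise would not disappear from the data.

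A reader might infer more than the documents support:

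- *That a between-arm severity comparison, or the safety comparison as a whole, is undermined.* None is specified by intensity. Section 10.0 promises standard summaries and listings, and the SAP names tests only for clinical cure.
- *That rescue events as a class cannot be graded.* Section 6.4 names glaucoma, not a pressure rise, and does not say that any trigger leaves activities unimpaired. Some may, but that is an assumption.
- *That the trial's monitored findings generally have no grade.* SPK that needs no treatment and does not limit activities is plainly Mild.
- *That the small arms make the defect large.* The weight of one reclassified subject reflects arm size under any scale and says nothing about this table.

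**Conclusion.** The point stands as a minor one. A mandatory grading rule gives no grade to two kinds of event, and it leaves the boundary between Moderate and Severe to the grader for a third. The consequence is limited to tabulations and listings of AEs by intensity. AE incidence, seriousness, pressure, SPK and rescue data, and the primary endpoint, are untouched.

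The size cannot be given, because the documents state no expected AE rates. Grading is meant to be masked, so arbitrary choices should mostly add noise. Treated pressure findings without a grade could fall more often in the steroid arm, but nothing in the documents allows that to be quantified.

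The conclusion assumes that impairment and departure from activities are the same criterion, and that some treated findings do not limit activities. It also assumes that no grading rule stands in section 10.6.6, on reporting of serious events, which the contents list but whose text is not available here.

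**What to change.** Reword the three definitions on one axis, the degree to which usual activities are impaired, so that every event has exactly one grade. For example: Mild, no impairment, including findings seen only on examination; Moderate, some impairment; Severe, unable to carry out usual activities.

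Add one field to the AE form for treatment given: none, medication, study drug stopped, or rescue. List treated or rescued events separately whatever their intensity. The separate listing matters, because on an impairment axis a treated pressure rise that does not limit activities becomes Mild and would otherwise be lost among trivial events.

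The cost is the wording of section 10.6.3, one form field and one listing, with no added visit or procedure. The price in content is that the grade would no longer reflect the need for treatment, and the new field is there to carry that information. No rule on rescue or on stopping treatment needs to change.

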10.6.4 Eliciting Adverse Events

At each study visit the subject will be questioned about AEs. All AEs, whether observed by the Investigator, elicited by the Investigator or designee, or spontaneously reported by the subject will be documented in the subject's chart and the Adverse Event Reporting Form. The investigator must assess whether or not the AE is related to the study drug, and to determine whether to continue or discontinue the study drug.

10.6.5 Serious Adverse Events

Each AE is to be classified by the Investigator as SERIOUS or NON-SERIOUS.

11.0 Statistical Considerations

The clinical success rate is expected 50%-75% higher in the treatment group than in the placebo group. The microbiological cure rate is expected to be 60%-80% higher in the treatment drug arm compared to the placebo arm. Based on these estimates of efficacy, statistical and clinical significance will be demonstrable with 30 patients in each group to assure an outcome analysis with a power of >80% to detect the difference between the two groups at the 95% confidence interval.

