Eligibility Criteria	
Inclusion Criteria
 
 • Conjunctivitis (as defined below) within 72 hours of initial ocular symptoms. • At least 18 years of age. • Subjects capable of understanding the purpose and risks of the study, and able to give informed consent. • Conjunctivitis diagnosis defined as presence of the two cardinal signs of acute conjunctivitis- 1) bulbar conjunctival injection and 2) conjunctival discharge/exudates. • A three-point rating scale (0=absent, 1=mild, 2=moderate, 3=severe) will be employed to grade conjunctival discharge/exudates. • All patients will require a rating of 1(mild) or greater for conjunctival discharge/exudates. • Patients will require a rating of 1 (mild) for bulbar conjunctival injection.
	
Exclusion Criteria
 
 • Conjunctivitis greater than 72 hours after initial ocular symptoms • Corneal ulcer, endophthalmitis, or any other confounding infection of the eye • Patients taking topical anti-inflammatory medications on a chronic basis • Known steroid glaucoma responders • Active herpes ocular infection • Pregnant women • Known allergy to chlorhexidine
Trial Design	This is a phase II single-center, prospective, placebo-controlled, randomized study of SCH1 in the treatment of acute infectious conjunctivitis. Study drug will be evaluated against vehicle.
Primary Endpoint	Clinical cure defined as rating of 0/3 for bulbar conjunctival injection and 0/3 for conjunctival exudates/discharge or clinical success defined as an overall decrease by 3 in the sum of both grades.

Secondary	
 Patients will keep a self log of symptom score each of the 5 days of the study
Number of Subjects	
 30 (15 per treatment arm)
Target Population	
 Patients with infectious conjunctivitis defined by bulbar conjunctival injection (rated at least 1 on 3 point grading scale) and conjunctival exudates / discharge (rated at least 1 on 3 point grading scale). Patients greater than one year of age. Patients of any race or ethnic group.
Length of Study	
Enrollment period: 12 months Treatment period: 5 days Overall duration: 6 months 5 days

Study Drug	
Subjects will be randomized to one of the following treatment arms: Treatment Arm A: SCH1 Treatment Arm B: Placebo (Vehicle only)

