5.0 Trial Design

This is a Phase II single-center, double-masked, placebo controlled, randomized study of SCH1 for the treatment of infectious conjunctivitis. Approximately 30 subjects will be enrolled, who will be randomized in a 1:1 ratio between SCH1 and placebo. Subjects will be assessed at day 1, day 3, and day 5 for efficacy and safety.

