Descriptive statistics (i.e. mean and standard deviations [SD] for normally distributed data, median with interquartile ranges [IQR] for non-normally distributed data) were calculated for all relevant measures. Percentage breakdowns will be used for categorical variables (ie: gender, age). All P-Values will be two-sided with statistical significance evaluated at the 0.05 alpha level.

All analyses were performed in SAS Version 9.4 (SAS Institute, Inc. Cary, NC).

Determination of Sample Size

The determination of sample size was derived from clinical experience, in which we expected the clinical cure rates at day 5 to be approximately 20% and 80 % in the placebo and SCH-1 groups respectively. A sample of 15 patients per group will yield 87% power to detect a difference between 20% and 80%, based on a Fisher's exact test with a 0.05 significance level.

Changes in the Conduct of the Study or Planned Analyses

There were no changes in the conduct of the study or planned analysis.

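### Section 11.0 ties its power of more than 80% to 30 patients per group, but the trial randomises about 15 per arm, where that power is not assured across the stated effect range

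*Combined protocol and SAP*

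**What the plan says.** Protocol Section 11.0 sets out two expected effects. For clinical success: "The clinical success rate is expected 50%-75% higher in the treatment group than in the placebo group". For microbiological cure: "The microbiological cure rate is expected to be 60%-80% higher in the treatment drug arm compared to the placebo arm". From these it concludes that "statistical and clinical significance will be demonstrable with 30 patients in each group to assure an outcome analysis with a power of >80"%. The confidence level named there is 95%. The section gives no placebo rate, does not say whether the percentages are points or ratios, and names no test.

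Every other statement of size is half of this:

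- The Synopsis, under number of subjects, gives "30 (15 per treatment arm").
- Section 5.0: "Approximately 30 subjects will be enrolled, who will be randomized in a 1:1 ratio between SCH1 and placebo". Section 5.1 repeats the total and the ratio.
- The SAP, under determination of sample size: "A sample of 15 patients per group will yield 87% power to detect a difference between 20% and 80"%, by Fisher's exact test at the 0.05 level. The rates are for clinical cure at day 5.

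The SAP defines clinical cure as a score of zero on both signs. Section 4.1 and the Synopsis also count a fall of 3 in the summed grades, and the Synopsis calls the combined outcome the clinical success rate. The SAP's analysis section allows chi-square or Fisher's exact tests, two-sided at 0.05, and the SAP closes by reporting no changes to the planned analysis.

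**The concern.** The protocol contains two sample sizes that differ twofold, and Section 11.0 attaches its power claim to the one that is not being run. Both stand in current text, so this is not a trace of an amendment.

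The SAP's separate calculation does not settle the matter. It covers a single 60-point difference, whereas Section 11.0's range for clinical success starts at 50. It also concerns a narrower endpoint than the one Section 11.0 describes. Someone reading Section 11.0 alone would credit this 30-patient trial with more than 80% power over the whole expected range, and could weigh a null result accordingly.

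**Working it through.** **Inputs.** Enrolled size 15 per arm (Synopsis; Sections 5.0 and 5.1; SAP). Section 11.0 size 30 per group, so 2 × 30 = 60 patients. Two-sided α = 0.05 (SAP). Fisher's exact test as the SAP's stated basis for power, with chi-square as the alternative it allows for analysis. Low and high ends of the clinical success effect, 50 and 75 (Section 11.0), read as percentage points. Section 11.0 gives no placebo success rate. The SAP's 20% placebo *cure* rate is borrowed as an assumption and then varied.

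**Formula.** With n per arm and true rates p₀ (placebo) and p₁ (SCH1), exact power is

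power = Σₐ Σᵦ Bin(a; n, p₀) · Bin(b; n, p₁) · 1{p-value(a, b) ≤ 0.05},

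summed over all (n + 1)² tables: 16 × 16 at n = 15 and 31 × 31 at n = 30.

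**Step 1: the SAP figure.** n = 15, 20% versus 80%, two-sided Fisher: 87.2%. The stated 87% reproduces.

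**Step 2: the Section 11.0 figure at its own size.** n = 30, 20% versus 70% (50 points), Fisher: 97.1%. A claim of more than 80% is therefore true for 30 per group on the percentage-point scale.

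**Step 3: the same range at the enrolled size (n = 15, placebo 20%).**

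| Rates | Difference | Power, Fisher |
|---|---|---|
| 20% vs 70% | 50 points | 68.0% |
| 20% vs 75% | 55 points | 78.5% |
| 20% vs 80% | 60 points | 87.2% |
| 20% vs 95% | 75 points | 99.4% |

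**Step 4: sensitivity to the placebo rate (50 points, n = 15, Fisher).**

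| Placebo rate | 5% | 10% | 20% | 25% | 30% | 40% | 45% |
|---|---|---|---|---|---|---|---|
| Power | 82% | 74% | 68% | 68% | 68% | 74% | 82% |

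**Step 5: sensitivity to the test (20% vs 70%, n = 15).** Uncorrected chi-square by the same enumeration: 81.5%. Chi-square when all expected counts are at least 5, otherwise Fisher: 80.5%. That switching rule is an assumption, because the SAP does not define its validity condition. The margin over 80% is thin: with 14 evaluable per arm, chi-square gives 77.2%, and neither document states a dropout allowance.

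**Step 6: microbiological cure.** Its range starts at 60 points. At n = 15 Fisher power for 60 points is at least 87% at every placebo rate tried from 5% to 40%, if all 15 per arm contribute. The shortfall is confined to the low end of the clinical success range.

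**The case against.** The strongest reply is that the enrolled size already has a sound basis. The SAP gives rates, test and α for 15 per group, its figure is right, and powering on one assumed difference is ordinary practice. On this view Section 11.0 is a drafting slip. That stands as far as it goes: the design is not without a power calculation. It does not remove the contradiction, and the SAP figure cannot simply stand in for Section 11.0, because it is for clinical cure. A patient who is cured also counts as a success, so the placebo success rate cannot be below the placebo cure rate and may exceed it. The 20% used above is therefore a borrowed figure.

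The second reply is that the low-end shortfall depends on the test. This is correct. Under chi-square, power at 20% versus 70% is just over 80%. Fisher is the basis the SAP chose for its power statement, so 68% is the like-for-like figure, but it is not the only one the analysis plan permits.

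A reader might go further in three ways that the documents do not support:

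- **That Section 11.0's arithmetic is false.** It holds for 30 per group in percentage points; the trial does not enrol that number.
- **That the trial plainly falls below 80% power.** This holds at the low end under Fisher for placebo rates of about 10% to 40%, not under every permitted test or placebo rate.
- **That the percentages are relative increases, which would leave very little power.** Section 11.0 does not exclude this, but the SAP's gap of 80 − 20 = 60 points lies inside 50 to 75 and favours the absolute reading. As a relative increase it would be (80 − 20)/20 = 300%. The scale should be stated; no conclusion should rest on the relative reading.

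**Conclusion.** Section 11.0 is wrong as written. Its sample size is twice the one planned everywhere else, and its power claim belongs to that larger size. It also leaves out the placebo rate, scale and test, and it addresses endpoints other than the one the SAP powers.

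At 15 per arm, power for a 50-point difference is 68% by two-sided Fisher if placebo success is 20%. It is about 68% to 74% for placebo rates of 10% to 40%, and 82% at 5% or 45%. The uncorrected chi-square gives 81.5% at 20% versus 70%. More than 80% is therefore not assured across Section 11.0's range for clinical success. The contradiction in size rests on the text alone. The size of the shortfall rests on the percentage-point reading, the assumed placebo rate, the choice of test and no dropout.

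**What to change.** Rewrite the sample size statement in Section 11.0:

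- Delete the 30-per-group figure and the unqualified claim of more than 80% power.
- State 15 per arm, the endpoint being powered (clinical cure, or cure or a 3-point fall), the assumed absolute rate in each arm, and the test.
- Give the SAP's 87% for 20% versus 80% by Fisher, labelled as clinical cure.
- For the 50-point low end, give 68% (Fisher) and 81.5% (uncorrected chi-square), marked as resting on an assumed 20% placebo success rate.

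Copying the SAP paragraph into Section 11.0 without naming the endpoint would hide the mismatch between cure and success. The change is wording only and asks for no extra enrolment. Its cost is a less favourable stated power at the low end of the range.
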